## Appendix 3: Health Screening Questionnaire

Please answer all questions on this form (answer n/a where not applicable). Please do not leave blanks on the form.

### Personal Details

Name: \_\_\_\_\_

Email Address: \_\_\_\_\_

Address: \_\_\_\_\_

Mobile Number: \_\_\_\_\_

Date of Birth: \_\_\_\_\_

Occupation: \_\_\_\_\_

Height: \_\_\_\_\_

Weight: \_\_\_\_\_

Ethnicity: \_\_\_\_\_

Gender: \_\_\_\_\_

Age: \_\_\_\_\_

### Health and Medical History

1. Are you currently taking any prescription or over-the-counter medications, not including vitamins or herbal supplements? ☐ Yes ☐ No  
If yes, please list: \_\_\_\_\_

2. Are you currently taking any prescription psychiatric or neurologic medication (including MAO inhibitors or SSRIs)?

Examples: phenelzine, tranylcypromine, sertraline, fluoxetine, lithium, valproate, carbamazepine.

☐ Yes ☐ No

3. Are you currently on immunosuppressive therapy?

Examples: Calcineurin inhibitors, mTOR inhibitors, Antimetabolites (antiproliferatives), Corticosteroids, Alkylating agents (cytotoxic immunosuppressants), Biologic agents (monoclonal antibodies & fusion proteins).

☐ Yes ☐ No

4. Do you have any known food allergies or intolerances? ☐ Yes ☐ No

If yes, please specify: \_\_\_\_\_

5. Do you have any of the following medical conditions? (check all that apply)

- ☐ Psychiatric conditions (e.g., depression, anxiety, bipolar disorder)  
☐ Neurologic disorders (e.g., epilepsy, seizure disorders, Parkinson's disease, multiple sclerosis)  
☐ Endocrine disorders (e.g., diabetes, thyroid disorders, adrenal disorders)  
☐ Cancer (active, under treatment, or treated within the past 5 years)

6. Have you experienced a significant cardiovascular event in the past 6 months (e.g., heart attack, stroke, coronary bypass, angioplasty)? ☐ Yes ☐ No

7. Are you pregnant, planning to become pregnant, or currently breastfeeding? ☐ Yes ☐ No

8. Please use the space below for any other health information you believe is relevant:

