## OUTCOMES

### Primary Objective

To assess between-group differences in the change in blood Vitamin C levels from baseline to Day 28 following supplementation with Qualia Vitamin C+ versus placebo.

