# NUMBER OF PARTICIPANTS

Number of Participants: Approximately 36 total (18 in each arm)

---

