## Inclusion / Exclusion Criteria

Inclusion criteria:

Provide voluntary, written, informed consent to participate in the study.

Agree to provide a valid cell phone number and are willing to receive communications through text.

Can read and write English.

Willing to complete questionnaires, records, and diaries associated with the study.

Healthy male and female participants aged 25 years or older.

Willing to go to an Ulta Labs Patient Service Center location for a Blood Vitamin C Test (baseline and Day 29) and located within a convenient distance of participating locations. [Note: The services offered by Ulta Lab Tests are available only in the United States and not to residents of the states of New Jersey, New York, and Rhode Island.]

Willing to avoid starting new or stopping any existing dietary supplements throughout the study.

Exclusion criteria:

Women who are pregnant, breastfeeding, or planning to become pregnant or start breastfeeding during the trial.

Known food intolerances/allergy to any ingredients in the product.

Having any of the following conditions: Psychiatric conditions, neurologic disorders, endocrine disorders, cancer.

Having had a significant cardiovascular event in the past 6 months.

Taking MAO inhibitors, SSRIs, or any other psychiatric or neurological medicines  
On immunosuppressive therapy.

Adults lacking capacity to consent.

---

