## Randomization And Blinding

Participants will be randomized in a 1:1 ratio to one of two study groups: Qualia Vitamin C+ or placebo. To maintain double-blinding, a designated Qualia Life Sciences staff member independent of the research team will assign and label all study products as A or B. Both participants and study personnel will remain blinded to group assignments until study completion. Unblinding will occur only after all study data have been collected and finalized.

---

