## Statistical Methodology

Data will be assessed for normality using the Shapiro-Wilk test and by evaluating skewness and kurtosis. Descriptive statistics will be reported as mean (SD) for continuous variables and frequencies (percentages) for categorical variables. For each outcome, changes from baseline will be computed at subsequent time points, and paired t-tests or linear mixed-effects models will be used to evaluate within-group differences. Between-group comparisons will be conducted using linear mixed-effects models with fixed effects for group, time, and their interaction, and a random intercept for participants to account for repeated measures. Data that do not meet the assumptions of normality will be analyzed using appropriate non-parametric statistical tests. Estimated coefficients, 95% confidence intervals, and p-values for interaction terms will be extracted at each time point. Moderator variables will be considered in adjusted models. Analyses will be performed using Python (statsmodels). The sample size was estimated to yield 80% power to detect an effect size (Cohen's  $d = 0.80$ ) with a two-tailed t-test at a 0.05 significance level.

---

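### Current vitamin C users are neither excluded nor systematically identified and must keep taking their products; users in the active arm may attenuate the primary contrast by an unknown amount

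*Combined protocol and SAP*

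**What the plan says.** The primary objective is a between-group comparison of change: "To assess between-group differences in the change in blood Vitamin C levels from baseline to Day 28" "following supplementation with Qualia Vitamin C+ versus placebo" (Primary Objective).

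On participants' own supplements, the protocol says the following.

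- **Eligibility.** No exclusion criterion names vitamin C, multivitamins or any other supplement. One inclusion criterion reads "Willing to avoid starting new or stopping any existing dietary supplements throughout the study" (Inclusion / Exclusion Criteria), so a current user stays on the product.
- **Screening form.** Question 1 in Appendix 3 (Health and Medical History) reads "Are you currently taking any prescription or over-the-counter medications, not including vitamins or herbal supplements". No later question asks about supplements. Only the closing free-text item could bring one to light, by chance.
- **During the study.** Apart from an open comment box, the check-in in Appendix 2 concerns the study product only.
- **Baseline test.** The vitamin C test must be completed before product is shipped (Study Schedule), but no level affects eligibility.
- **Draw timing.** Outcome Measures asks for an overnight fast. The note to the Day 29 assessments adds an interval of about 18 to 24 hours after the last study dose. Neither mentions the participant's own supplements.
- **Allocation and analysis.** Stratification is by gender and age. Statistical Methodology allows moderators in adjusted models but names none.

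**The concern.** A participant's own vitamin C is the most direct influence on the primary endpoint other than the study product. The plan permits it, requires it to continue and does not systematically record it. Two consequences follow.

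First, a user allocated to the active product may start from a higher level and gain less. The average active-arm change would then be smaller than in non-users, and so would the contrast with placebo.

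Second, the Day 29 note explains that the interval after the last dose is there to avoid the short-lived rise that follows a dose. By the same reasoning, a participant in either arm who takes their own vitamin C shortly before one draw but not the other adds error to the change score.

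Interpretation is also at stake. If the plan is followed as written, a null result could not be told apart from enrolment of people who were already supplemented, and a positive result could not be described separately for users and non-users.

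**Working it through.** **Inputs from the documents.** "Number of Participants: Approximately 36 total (18 in each arm"); 1:1 allocation; d = 0.80, 80% power, "with a two-tailed t-test at a 0.05 significance level" (Number of Participants; Randomization And Blinding; Statistical Methodology).

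**Inputs assumed, because the documents do not give them.** f is the share of participants who are current users, equal in both arms on average. r is a user's response to the active product relative to a non-user's (0 = no further gain, 1 = full response).

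**Step 1: the plan's own figure.** A two-sided two-sample t-test at d = 0.80 needs 25.5, so 26 per arm (52 in total), for 80% power. The normal approximation gives 25 per arm. At 18 per arm, power is 64.5% (t) or 67.0% (normal). The stated 80% is therefore not reproduced. That is a separate defect; 64.5% serves here only as the starting point.

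**Step 2: which users matter.** Expected contrast = mean change on active − mean change on placebo.

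- Placebo: a user with stable intake has an expected change of about 0, as does a non-user, so the placebo mean stays at 0 whatever f is.
- Active (in SD units): (1 − f) × 0.80 + f × r × 0.80.
- Hence d_eff = 0.80 × (1 − f × (1 − r)).

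A simulation under these assumptions (40,000 trials, 18 per arm) gave:

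| Users | Mean contrast | Power |
|---|---|---|
| None | 0.80 | 64.4% |
| 30% of placebo arm only | 0.80 | 64.8% |
| 30% of active arm only, r = 0 | 0.56 | 35.2% |
| 30% of both arms, r = 0 | 0.56 | 35.4% |

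The second row follows from the assumption of stable intake; the simulation does not test that assumption.

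**Step 3: size.** Two-sample t-test, 18 per arm, SD held constant:

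| f | d_eff, r = 0 | Power | d_eff, r = 0.5 | Power |
|---|---|---|---|---|
| 20% | 0.80 × 0.80 = 0.64 | 46.3% | 0.80 × 0.90 = 0.72 | 55.5% |
| 30% | 0.80 × 0.70 = 0.56 | 37.2% | 0.80 × 0.85 = 0.68 | 50.9% |
| 40% | 0.80 × 0.60 = 0.48 | 28.8% | 0.80 × 0.80 = 0.64 | 46.3% |

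With r = 1, d_eff stays at 0.80 and power at 64.5%. Allowing for the extra spread from mixing users and non-users in the active arm lowers the r = 0 figures slightly, to 44.4%, 35.2% and 27.1%.

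**Step 4: chance imbalance.** With the number of users in each arm binomial (18, f), the probability that the arms differ by three or more users is 29%, 36% and 40% at f = 20%, 30% and 40%.

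**The case against.** The strongest defence is that continuing stable supplements is a legitimate add-on design. The primary objective compares product with placebo in healthy adults and does not restrict the question to non-users. Holding background intake constant is also what keeps the placebo change near zero. This stands: admitting users is not in itself an error, and it does not put the trial off its stated question.

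Other parts of the defence limit what can be claimed.

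- A reader might infer that supplemented placebo participants dilute the contrast. With a change score and stable intake they do not (Step 2).
- A reader might take the survey figures in the Introduction as proof of limited headroom. They leave 100 − 14 − 20 = 66% of men and 100 − 10 − 17 = 73% of women in the normal range. But normal there means only above 28 µmol/L, a lower cut-off with no ceiling, and the figures describe vitamin C status, not supplement use.
- A reader might conclude that adjustment is impossible. Baseline vitamin C is measured in everyone and reflects starting level directly. It does not show source, amount or time of last intake, and the plan does not commit to using it.
- The r = 0 column is the worst case. The plan also does not say that d = 0.80 refers to non-users; it could already be an average over a mixed population.
- Uneven numbers of users would be chance imbalance under randomisation, costing precision. It is not systematic bias.
- The overnight fast gives partial control over the draws, though neither instruction mentions participants' own supplements.

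**Conclusion.** The concern holds in a conditional form. It is certain from the documents that users can enter either arm, must continue, and are not systematically identified at screening or on study. That the contrast is attenuated is only possible: it requires users in the active arm with a reduced response, and neither their number nor their response is known. Taking d = 0.80 as the non-user effect with constant SD, power at 18 per arm lies anywhere from 64.5% (full response) down to 28.8% (40% users with no gain). A half response gives 46% to 56% over user shares of 20% to 40%. Because 18 per arm already falls short of 80%, there is no margin to absorb a loss. The extra error from own vitamin C taken near one draw cannot be sized from the documents.

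The documents do not support saying that the contrast is diluted as a fact, that placebo users cause it, or that the comparison is biased. This is a cheap improvement to precision and interpretability.

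**What to change.** 1. **Appendix 3:** add a question on current use of vitamin C, a multivitamin or any other product containing vitamin C, with product, amount and frequency.
2. **Both blood draws:** repeat the question and record the time of last intake. This also checks that the rule on starting and stopping supplements was kept.
3. **Statistical Methodology:** pre-specify baseline vitamin C and user status (yes/no) as covariates in the primary model. With only two draws, the simple form is a regression of the Day 29 value on arm, baseline and user status. A user main effect merely added to the planned mixed model would not change the group-by-time estimate with complete data. Tabulate users by arm.

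These steps improve precision and make the result readable; they do not restore a contrast that users have reduced. Excluding regular users is an option for the sponsor to weigh against recruitment and generalisability. A third stratification factor is not recommended: even if all three factors were binary there would be 8 cells, and 36 / 8 = 4.5 participants per cell.

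Cost: a few questionnaire items, an IRB amendment, and one or two model degrees of freedom.

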## Appendix 4: Overall Experience Questionnaire

### Background

These questions are intended to capture information that may be used for product evaluation and marketing and will be asked 5-7 days after the final dose of the test product.

## Questions and Answers

1. What was your overall experience of the product, keeping in mind the intended primary use is to promote healthy Vitamin C levels?

- a. Excellent
- b. Good
- c. No effect
- d. Poor
- e. Very poor

2. How would you rate the product ?

- a. 5 stars
- b. 4 stars
- c. 3 stars
- d. 2 stars
- e. 1 star

3. Is this a product you'd be interested in purchasing?

- a. Yes
- b. Maybe
- c. No

4. Please describe your experience with this product.

Note: this will be a text box

5. Please give the review of your experience a several word title.

Note: this will be a text box

6. While taking this, did you come in contact with someone who had a cold, the flu, or other contagious respiratory infections?

- a. Yes
- b. No

7. If you answered yes to the question above, did you become sick after being in contact with the person?

- a. Yes
- b. No
- c. N/A

8. Do you think your capacity to respond to circumstances that challenge the immune system (such as being around people with colds or flu, travel, lack of sleep, etc.) was improved while you were taking this product?

- d. Yes
- e. No

## Scoring

Each question will be evaluated individually.

An average will be produced for the responses to question 2.

## Appendix 5: PROMIS Cognitive Function v2.0 - Short Form 8a

### Background

Patient-Reported Outcomes Measurement Information System (PROMIS) is a system of questionnaires developed by the National Institutes of Health (NIH) to create reliable and precise measures of patient-reported health status. The Cognitive Function It assesses a person's health through a series of questions about what they can do and how they feel. The four-, six -, and eight-item short form of the PROMIS® v2.0 Cognitive Function scale v2.0 - Short Form 8a assess subjective cognitive functioning. This scale has strong internal consistency reliability, supporting its use as a reliable measure of subjective cognitive functioning.

### Questions and Answers

Please respond to each question based on your experience in the past 7 days. Mark one box per row, using the following scale: 5 = Never, 4 = Rarely (Once), 3 = Sometimes (Two or three times), 2 = Often (About once a day), 1 = Very often (Several times a day)

1. My thinking has been slow.
2. It has seemed like my brain was not working as well as usual.
3. I have had to work harder than usual to keep track of what I was doing.
4. I have had trouble shifting back and forth between different activities that require thinking.
5. I have had trouble concentrating.
6. I have had to work really hard to pay attention or I would make a mistake.
7. I have had trouble forming thoughts.
8. I have had trouble adding or subtracting numbers in my head.

### Scoring Instructions

The scoring manual for is available at  
[https://www.healthmeasures.net/images/PROMIS/manuals/Scoring\\_Manual\\_Only/PROMIS\\_Cognitive\\_Function\\_Scoring\\_Manual\\_17Mar2022.pdf](https://www.healthmeasures.net/images/PROMIS/manuals/Scoring_Manual_Only/PROMIS_Cognitive_Function_Scoring_Manual_17Mar2022.pdf)

Each response is scored on a 5-point scale:

- Never = 5
- Rarely = 4
- Sometimes = 3
- Often = 2
- Very often = 1

Step 1: Assign each response the appropriate score.

Step 2: Sum the scores across all 8 items to calculate the Raw Score. The minimum possible raw score is 8 and the maximum possible raw score is 40.

Step 3: Use the conversion table below to translate the Raw Score into a T-score and Standard Error (SE).

**Adult v2.0 – Cognitive Function 8a Short Form Conversion Table**

Raw Score	T-Score	Standard Error (SE)
8	23.27	4.36
9	26.59	3.47
10	28.63	3.13
11	30.23	2.93
12	31.63	2.76
13	32.87	2.64
14	34.01	2.56
15	35.07	2.51
16	36.07	2.48
17	37.04	2.46
18	37.97	2.45
19	38.9	2.44
20	39.81	2.44
21	40.71	2.44
22	41.61	2.45
23	42.51	2.46
24	43.42	2.46
25	44.34	2.48
26	45.27	2.49
27	46.21	2.5

28	47.18	2.52
29	48.16	2.53
30	49.17	2.55
31	50.21	2.56
32	51.29	2.59
33	52.42	2.63
34	53.63	2.68
35	54.94	2.78
36	56.39	2.93
37	58.03	3.14
38	59.95	3.41
39	62.52	3.9
40	67.09	5.24

## Appendix 6: Perceived Stress Scale 10 (PSS-10)

### Background

Since Vitamin C and Bioflavonoid consumption is associated with reduced stress/improved mood, using a validated questionnaire to assess stress will be essential. The Perceived Stress Scale (PSS) is the most widely used psychological instrument for measuring the perception of stress. The original version has 14 questions. The 10-item version is also widely used (and is below). It is a measure of the degree to which situations in one's life are appraised as stressful, with questions designed to tap into how unpredictable, uncontrollable, and overloaded respondents find their lives. Because levels of appraised stress should be influenced by daily hassles, major events, and changes in coping resources, predictive validity of the PSS is expected to fall off rapidly after four to eight weeks. The psychometric validations have all been on a 4 week recall (e.g., In the last month, how often have you been upset because of something that happened unexpectedly?). According to [this resource](#), making the recall period shorter is not expected to be a problem. So, I'd recommend changing the recall period to 1 week.

**INSTRUCTIONS:** The questions in this scale ask you about your feelings and thoughts during the last week. Indicate how often you felt or thought a certain way.

## Questions and Answers

1. In the last week, how often have you been upset because of something that happened unexpectedly?
2. In the last week, how often have you felt that you were unable to control the important things in your life?
3. In the last week, how often have you felt nervous and “stressed”?
4. In the last week, how often have you felt confident about your ability to handle your personal problems?
5. In the last week, how often have you felt that things were going your way?
6. In the last week, how often have you found that you could not cope with all the things that you had to do?
7. In the last week, how often have you been able to control irritations in your life?
8. In the last week, how often have you felt that you were on top of things?
9. In the last week, how often have you been angered because of things that were outside of your control?
10. In the last week, how often have you felt difficulties were piling up so high that you could not overcome them?

Answers: Never; Almost Never; Sometimes; Fairly Often; Very Often

## Scoring

PSS scores are obtained by using the following scoring for questions 1-3, 6, 9 & 10: Never = 0; Almost Never = 1; Sometimes = 2; Fairly Often = 3; Very Often = 4.

For the four positively stated items (items 4, 5, 7, & 8) use reverse scoring (e.g., Never = 4, Almost Never = 3, Sometimes = 2, Fairly Often = 1 & Very Often = 0). Scores are summed to get a total score.

Norm Table for the PSS 10 item inventory based on L. Harris Poll gathered information on 2,387 respondents in the U.S.

### By Gender

- Male = 12.1
- Female = 13.7

### By Age

- 18-29 = 14.2
- 30-44 = 13.0
- 45-54 = 12.6
- 55-64 = 11.9
- 65 & older = 12.0

## Appendix 7: Single-Item Assessment of Immune Fitness

### Background

Vitamin C status impacts immune system function, an assessment of immune fitness is warranted. The assessment of momentary and retrospective immune fitness can be conducted using a single-item patient-reported outcome measure. This single-item assessment of immune fitness was first used in 2015 in survey research conducted at Utrecht University in the Netherlands. The measure has been used subsequently in a number of studies. The single-item approach provides a global assessment that evaluates the entire constellation of immune fitness, regardless of the individual components contributing to it, in terms of the presence of immune-related complaints, their severity, and their impact.

### Questions and Answers

Note: Q&A should look like the below image.

### Rate your immune fitness

Immune fitness refers to the capacity of the body to respond to health challenges (such as infections) by activating an appropriate immune response, essential to maintain health, prevent and resolve disease, and improve quality of life

**At this moment, I rate my immune fitness as follows:**

0	1	2	3	4	5	6	7	8	9	10
----------	----------	----------	----------	----------	----------	----------	----------	----------	----------	-----------

Very poor
Excellent

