### Secondary Objectives

To assess within-group and between-group differences in PROMIS Cognitive Function - Short Form 8a, Perceived Stress Scale-10 domain scores, and Single-item Assessment of Immune Fitness.

To assess within-group differences in the change in blood Vitamin C levels.

To evaluate side effect profiles using a custom Safety and Tolerability survey.

---

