Dietary supplementation with Vitamin C has been shown to enhance the body's antioxidant capabilities, support healthy immune functioning, cognition, stress resistance, and maintain Vitamin C stores in preclinical and early clinical studies. Furthermore, the combination of bioflavonoids may have an additive effect for supporting these functions. Qualia Vitamin C+ is a novel multi-ingredient formulation developed to enhance the body's Vitamin C reserves, decrease oxidative stress, support immune function, and promote systemic health. It contains a strategic blend of Vitamin C (from a blend of liposomal vitamin C, minerals ascorbates, and fruit extracts), bioflavonoids, and ferulic acid, designed to optimize vitamin C status and provide comprehensive support for metabolic processes underlying healthy responses to oxidative stress and immunity.

The primary aim of this randomized, double-blind, placebo-controlled parallel trial is to compare the effects of a Qualia Vitamin C+ formulation on blood Vitamin C levels in healthy adult participants over a 28-day intervention period. Secondary objectives include evaluating the impact of supplementation on cognition, stress, and immunity, as reflected by changes in scores on the PROMIS Cognitive Function - Short Form 8a, the Perceived Stress Scale-10, and the Single-item Assessment of Immune Fitness, as well as characterizing the safety and tolerability profile and overall participant experience of the formulation.

---

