## Study Schedule

Days 1-28 are when participants will take the test formulas or placebo.

Screening (prior to enrollment (Day -21 to -15): Complete online prescreen questionnaire and provide electronic informed consent.

Baseline Assessments (Day -14 to -7):

1. Conduct Ulta Labs Vitamin C Test
2. Complete PROMIS Cognitive Function - Short Form 8a
3. Complete Perceived Stress Scale-10
4. Complete Single-item Assessment of Immune Fitness
5. Complete Safety and Tolerability survey

Note: Successful completion of baseline assessments and conformation of lab draw are required to ship a participant the study product.

Day 7 Assessments: Complete Safety and Tolerability survey.

Day 14 Assessments:

1. Complete PROMIS Cognitive Function - Short Form 8a
2. Complete Perceived Stress Scale-10
3. Complete Single-item Assessment of Immune Fitness
4. Complete Safety and Tolerability survey

Day 21 Assessments: Complete Safety and Tolerability survey.

Day 29 Assessments:

1. Conduct Ulta Labs Vitamin C Test
2. Complete PROMIS Cognitive Function - Short Form 8a
3. Complete Perceived Stress Scale-10
4. Complete Single-item Assessment of Immune Fitness

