## Scoring

A single numerical score between 0 and 10 is produced from the answer, with higher scores indicating better self-rated immune fitness.

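### Immune fitness is compared between groups one momentary rating at a time, as an unadjusted change from a single baseline rating, so the contrast is noisier than necessary and covers the 28 days thinly

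*Combined protocol and SAP*

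**What the plan says.** The Introduction states: "Secondary objectives include evaluating the impact of supplementation on cognition, stress, and immunity, as reflected by changes in scores on" three questionnaires, the last being the single immune-fitness item. Secondary Objectives asks for both kinds of comparison: "To assess within-group and between-group differences in PROMIS Cognitive Function - Short Form 8a, Perceived Stress Scale-10 domain scores, and Single-item Assessment of Immune Fitness".

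Appendix 7 words the item as "At this moment, I rate my immune fitness as follows" and scores it simply: "A single numerical score between 0 and 10 is produced from the answer". Its background notes that another form exists: "The assessment of momentary and retrospective immune fitness can be conducted using a single-item patient-reported outcome measure". Only the momentary form is included. PROMIS (Appendix 5) and the PSS-10 (Appendix 6) each look back one week.

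The Study Schedule places the item at baseline (Day -14 to -7), Day 14 and Day 29. The surveys in between do not carry it, for example "Day 21 Assessments: Complete Safety and Tolerability survey"; Day 7 is the same. The check-in form in Appendix 2 has no immune-fitness question.

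Statistical Methodology computes changes from baseline and fits a mixed model with group, time, their interaction and a random intercept, taking interaction p-values at each time point. Moderators may enter adjusted models, but the baseline rating is not named as a covariate, and no contrast averaged over visits is specified.

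**The concern.** A rating with no recall window describes only the moment of answering. Taken once before treatment and twice afterwards, it says little about the weeks between. The analysis then uses these few ratings inefficiently. Each reported contrast is one day minus one baseline day, so the day-to-day variation of both ratings enters in full.

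At stake is precision. With 18 per arm, an avoidably wide interval on the only formal immunity measure makes a null result less informative. The within-group comparison has a further weakness: illness or recovery between the baseline day and Day 29, such as a seasonal shift, would look like change, with no control arm to remove it.

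**Working it through.** **The plan's own figure.** No SD, correlation or target difference is given for this item. The only sample-size figure is 36 in total for 80% power at d = 0.80 (two-sided 0.05), with the outcome unnamed. It does not reproduce: the two-sample t-test needs 26 per arm (52 in total), and 18 per arm gives 64.5% power. That is a separate matter. It is used here only for scale: at 18 per arm, the standardised difference detectable with 80% power is 0.96.

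**Inputs.** From the plan: one baseline rating, post-baseline ratings on Days 14 and 29, existing surveys on Days 7 and 21, 18 per arm, random-intercept model. Assumed: equal SD at all visits and equal correlation r between any two visits (the structure a random intercept implies), with r from 0.4 to 0.7. Variances below are per participant, in units of the squared rating SD.

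**Step 1, planned contrast.** With complete data, the interaction at Day 29 is the difference between arms in mean change. Variance of one change = 2(1−r).

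**Step 2, baseline as covariate.** Residual variance at Day 29 = 1−r². Ratio to Step 1 = (1−r²)/[2(1−r)] = (1+r)/2: 0.70 at r = 0.4 and 0.85 at r = 0.7, a cut of 30% to 15%.

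**Step 3, averaging k post-baseline ratings.** Change score: (1−r)(1+1/k), which is 2, 1.5 and 1.25 times (1−r) for k = 1, 2, 4. Baseline-adjusted: (1+(k−1)r)/k − r².

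| r | Day 29 change | Day 29 adjusted | Days 14, 29 mean, adjusted | Four-day mean, adjusted | SE ratio, four to two (adjusted) |
|---|---|---|---|---|---|
| 0.4 | 1.20 | 0.84 | 0.54 | 0.39 | 0.85 |
| 0.5 | 1.00 | 0.75 | 0.50 | 0.375 | 0.87 |
| 0.6 | 0.80 | 0.64 | 0.44 | 0.34 | 0.88 |
| 0.7 | 0.60 | 0.51 | 0.36 | 0.285 | 0.89 |

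For change scores the four-to-two SE ratio is √(1.25/1.5) = 0.913 at any r. Going from two ratings to four therefore lowers the SE by about 9% (change) or 11–15% (adjusted).

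**Step 4, scale.** Detectable Day 29 difference in rating SDs, ignoring the degree of freedom spent on the covariate:
- r = 0.4: 0.96 × √1.20 = 1.05 unadjusted; 0.96 × √0.84 = 0.88 adjusted.
- r = 0.7: 0.96 × √0.60 = 0.74 unadjusted; 0.96 × √0.51 = 0.69 adjusted.

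**Step 5, slow build-up.** If the effect grows linearly to Day 29, the four-day mean carries (7+14+21+29)/(4×29) = 17.75/29 = 61% of the Day 29 effect. The SE ratio of the adjusted four-day mean to adjusted Day 29 is √(0.39/0.84) = 0.68 at r = 0.4 and √(0.285/0.51) = 0.75 at r = 0.7. Signal-to-noise is then 0.61/0.68 = 0.90 and 0.61/0.75 = 0.82 of the adjusted Day 29 contrast, so averaging loses in that case.

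**Step 6, passing illness.** Assume illness probability p on a rating day of 3–10%, a drop D of 2–4 points, rating SD s of 1–2 and r = 0.6. Illness adds 2p(1−p)D² to 2s²(1−r).
- p = 5%, D = 2, s = 1.5: 0.38/(1.80+0.38) = 17% of the change variance.
- Mildest case (3%, 2, 2): 0.233/3.433 = 7%.
- Harshest case (10%, 4, 1): 2.88/3.68 = 78%.

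With the same illness rate in both arms, the simulated type I error of the between-group test (20,000 replicates, s = 1.5) was 4.8–4.9%.

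**The case against.** A reader might infer that a cold on Day 29 drives the immune result, or that daily fluctuation swamps any treatment difference. The documents do not support either. Allocation is randomised and blinded, so illness unrelated to treatment falls on both arms by chance; it widens the interval without biasing the contrast. No SD, illness rate or expected effect is given, and illness is the larger part of the variance only under the harsher assumptions in Step 6. Participants are also told that "Immune fitness refers to the capacity of the body to respond to health challenges", which is not the same as being ill today. If the product did reduce illness, illness on the day would be part of its effect. This objection stands in full for the between-group comparison.

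The period is not wholly uncovered. Questions 6–8 of the Overall Experience Questionnaire (Appendix 4) ask about sick contacts, becoming sick and perceived immune capacity while on product. They are asked once, without a baseline and outside the stated objective, so they help only in part.

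Change to the end of treatment is a legitimate target, and an average over treatment answers a different question. That also stands, and Step 5 shows the price of substituting one for the other.

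The extra surveys contribute less than a comparison with Day 29 alone suggests. For change scores, averaging the existing Days 14 and 29 already gives a 25% variance cut, against 37.5% with four ratings. With baseline adjustment in both, it gives 29–36% against 44–54% (r = 0.7 to 0.4). The increment over two visits is the fair measure of what the new ratings add.

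**Conclusion.** The point holds as one of efficiency and coverage, not bias. The planned between-group contrast leaves a free gain unused: baseline adjustment cuts the Day 29 variance by about 15–30%. Two further ratings lower the SE of an average-over-treatment contrast by about 9% (change score) or 11–15% (baseline-adjusted) relative to averaging the two existing visits. The within-group comparison is more exposed to passing illness and should be read accordingly.

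The sizes rest on assumed correlations of 0.4 to 0.7, equal at all spacings. If ratings a week apart correlate more strongly than distant ones, averaging gains less. They also assume that the mixed model is used; the plan's unspecified non-parametric fallback could drop the baseline adjustment unless it is written in.

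The single momentary baseline limits the gain whatever is added later, and extra momentary ratings still miss an illness that begins and ends between survey days. A null result on one self-rated item with 18 per arm would remain weak evidence about immunity after these changes. Severity is minor.

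**What to change.** 1. In Statistical Methodology, specify that immune fitness is compared between groups with the baseline rating as a covariate: post-baseline ratings as outcomes; group, day and group-by-day as fixed effects; a random intercept. Keep the Day 29 group difference as its own reported contrast, and have any non-parametric fallback retain the baseline adjustment. The cost is one sentence and no new data.

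2. In the Study Schedule, add the unchanged item to the existing Day 7 and Day 21 surveys. Pre-specify the baseline-adjusted mean of the Day 7, 14, 21 and 29 ratings as a supporting average-over-treatment contrast, and report Days 7 and 21 descriptively so that they add no further tests. Reading the new days only through separate p-values would add almost nothing to the Day 29 contrast.

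The cost of the second change is two extra answers per participant (72 for 36 participants) and the schedule revision. Its downside is that an average including Day 7 dilutes a slowly building effect, so it should not replace Day 29.
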